### **10.3. Definition of Dose Limiting Toxicity and Discontinuation of Therapy**

DLTs are AEs that occur within Cycle 1 and meet any of the following criteria:

1. Treatment-emergent Grade 4 or 5 AE related to ixazomib + abatacept + dex treatment (see exceptions listed in #4 below).

Roswell Park Protocol No.: I 47217

2. Treatment-emergent Grade 3 AE related to ixazomib + abatacept + dex (see exceptions listed in # 4 below).
3. Treatment-emergent Grade 3 seizures.

The above AEs are considered to be DLTs if they are judged probably or definitely associated with treatment. Should they occur, individual participants will be taken off study and no further injections will be given. Toxicity will be determined using the revised NCI Common Toxicity Criteria (CTC) version 5.0 for Toxicity and Adverse Event Reporting (<http://ctep.info.nih.gov>).

4. The following **will not** be considered DLTs:

- Non-hematologic AEs
  - Grade 3 fatigue lasting  $\leq$  7 days
  - Grade 3 or 4 fever or febrile neutropenia for  $\leq$  2 weeks
  - Grade 3 increase in transaminases for  $\leq$  2 weeks or Grade 4 increase in transaminases for  $\leq$  7 days
  - Grade 3 Tumor Lysis Syndrome (TLS) for  $\leq$  2 weeks
  - Grade 3 or 4 asymptomatic, non-hematological clinical laboratory abnormalities that return to  $\leq$  Grade 2 within 7 days or electrolyte abnormalities that resolve with replacement
  - Grade 3 diarrhea lasting  $\leq$  72 hours that does not require total parenteral nutrition (TPN), tube feeding, or hospitalization, and the toxicity resolves to less than grade 3 within 72 hours
  - Grade 3 nausea/vomiting lasting  $\leq$  72 hours that does not require total parenteral nutrition (TPN), tube feeding, or hospitalization, and the toxicity resolves to less than grade 3 within 72 hours
  - Grade 3 peripheral neuropathy
  - Grade 3 hyperglycemia, or Grade 4 that responds to insulin therapy
- Hematologic AEs
  - Grade 3 neutropenia of any duration or Grade 4 neutropenia lasting  $<$  14 days
  - Grade 3 or 4 lymphopenia
  - Grade 3 or 4 leukopenia
  - Grade 3 or 4 thrombocytopenia without bleeding or requiring platelet transfusion
  - Grade 3 or 4 anemia
  - Grade 3 or 4 B-cell aplasia and hypogammaglobulinemia

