**Table 3 Dose Modification Guidelines for Ixazomib**

Hematological Toxicities	Recommended Actions
Thrombocytopenia (Platelet Count)	
Platelet count less than 30,000/mm 	
 
Withhold ixazomib until platelet count is at least 30,000/mm^3.
 
Following recovery, resume ixazomib at the next lower dose.
 

Neutropenia (Absolute Neutrophil Count)	
Absolute neutrophil count less than 500/mm 	
 
Withhold ixazomib until absolute neutrophil count is at least 500/mm^3. Consider adding G-CSF as per clinical guidelines.
 
Following recovery, resume ixazomib at the next lower dose.
 

Non-Hematological Toxicities	Recommended Actions
Rash	
Grade † 2 or 3	
 
Withhold ixazomib until rash recovers to Grade 1 or lower.
 
Following recovery, resume ixazomib at the next lower dose.
 

Grade 4	
 
Discontinue treatment regimen.
 

Peripheral Neuropathy	
Worsening Peripheral Neuropathy over Baseline (Grade 2 with pain or Grade 3)	
 
Reduce ixazomib to the next lower dose. Reevaluate after 1 cycle, if improved or stable, continue at the reduced dose.
 

Grade 4 Peripheral Neuropathy	
 
Discontinue treatment regimen.
 

Other Non-Hematological Toxicities	
Other Grade 3 or 4 Non-Hematological Toxicities	
 
Withhold ixazomib. If attributable to ixazomib, resume at the next lower dose following recovery.
 

†Grading based on National Cancer Institute Common Terminology Criteria (CTCAE) Version 5.0.

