### **10.6.1. Stopping Rules for Chronic Toxicity**

Upon completion of the DLT assessment period, the same DLT/ AE criteria used during the DLT assessment period (see **Section 10.3**) for determining treatment discontinuation will be followed if a participant develops a treatment-related chronic toxicity.

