#### 19.4. Primary Analyses

The primary objective is to determine the therapeutic efficacy (as measured by response rate) of abatacept + ixazomib + dexamethasone in multiple myeloma patients who have relapsed after treatment with their first proteasome inhibitor-containing regimen (excluding ixazomib) and have not been treated with a second proteasome inhibitor.

Previous studies have demonstrated a response rate of approximately 30% for ixazomib + dexamethasone as second line therapy in this patient population (34). We hypothesize that the proposed treatment combination (abatacept + ixazomib + dexamethasone) will improve the second-line response rate in this patient population. Therefore, we will test the following hypotheses:

$$H_0: \pi = 0.3$$

$$H_A: \pi > 0.3,$$

where  $\pi$  is the true response rate, using a one-sided Binomial exact test. A total of n=19 patients will be enrolled and if T=9 or more patients have a response, then the treatment combination will be considered promising; otherwise the treatment combination is not promising. Additionally, the response rate will be summarized using a 90% confidence interval obtained using Jeffrey's prior method.

**Replacement:** Patients that withdraw from the study prior to completing the first cycle of treatment due to toxicity, disease progression, or other treatment related reasons will be considered as 'non-responders' and included in the primary analysis.

Patients that withdraw from the study prior to completing the first cycle of treatment due to non-treatment related reasons will be considered 'unevaluable' for the primary outcome and will be replaced.

**Efficacy Analysis:** Responses to treatment will be measured by serum immunoglobulins, serum free kappa and lambda light chains, serum protein electrophoresis/immunofixation electrophoresis, and 24-hour urine protein electrophoresis/immunofixation. International uniform response criteria will be used. The anti-myeloma activity will be evaluated on an exploratory basis

Roswell Park Protocol No.: I 47217

and will be summarized using descriptive statistics or graphical methods. No formal comparison will be carried forth

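### For probably or definitely related, non-excepted Grade 3-4 events in Cycle 1, Section 10.3 takes the patient off study while Table 3 holds and resumes ixazomib, and nothing says which governs

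*Combined protocol and SAP*

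**What the plan says.** Section 10.3 defines DLTs as Cycle 1 events of Grade 3, or of Grade 4 or 5, related to the combination, apart from a list of exceptions (item 4). It adds an attribution threshold: "The above AEs are considered to be DLTs if they are judged probably or definitely associated with treatment". The consequence is stated without qualification: "Should they occur, individual participants will be taken off study and no further injections will be given".

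Table 3 in Section 10.4.2 is introduced as the set of rules to be used for toxicity. For Grade 2 or 3 rash it says "Withhold ixazomib until rash recovers to Grade 1 or lower", followed by restarting at the next lower dose. For other Grade 3 or 4 non-hematological toxicity it says "Withhold ixazomib. If attributable to ixazomib, resume at the next lower dose following recovery".

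Section 10.6.1 states that, after the DLT period, the Section 10.3 criteria "for determining treatment discontinuation will be followed if a participant develops a treatment-related chronic toxicity".

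Section 19.4 deals with early losses. "Patients that withdraw from the study prior to completing the first cycle of treatment due to toxicity", or because of progression or another treatment-related reason, are kept in the primary analysis as non-responders. The regimen is called promising if at least 9 of 19 patients respond.

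**The concern.** A patient cannot be both off study and restarted on ixazomib at a lower dose. Where one event falls under both passages, two sites can each follow the protocol and handle that event in opposite ways. The trial is multi-site, so this is a practical possibility.

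The statistical stake is the primary count. A patient removed in Cycle 1 for toxicity is a non-responder by rule. The same patient managed under Table 3 stays on treatment and may respond. With a cut-off of 9 of 19, one patient classified differently can move the result from 8 to 9 or back.

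**Working it through.** **Step 1. Where the two passages overlap.** For a Cycle 1 event judged probably or definitely related:

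| Event | Section 10.3 | Table 3 | Conflict |
|---|---|---|---|
| Grade 3 rash | Not excepted; off study | Hold, resume one level down | Yes |
| Other non-excepted Grade 3-4 non-hematological events, e.g. Grade 3 diarrhea or vomiting beyond 72 hours, Grade 3 fatigue beyond 7 days | Off study | Hold; resume one level down if attributable to ixazomib | Yes |
| Grade 4 neutropenia of 14 days or more | Not excepted; off study | Hold and resume if the count is below 500/mm³ | Yes, narrow case |
| Grade 3-4 thrombocytopenia with bleeding | Exception does not cover it; off study | Hold and resume if the count is below 30,000/mm³ | Yes, narrow case |
| Grade 3 neuropathy, Grade 3 neutropenia, Grade 4 neutropenia under 14 days, thrombocytopenia without bleeding | Excepted | Table 3 alone | No |
| Grade 4 rash, Grade 4 neuropathy | Off study | Regimen discontinued | No |

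Grade 2 rash, and any event judged only possibly related, is never a DLT, so Table 3 alone applies.

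**Step 2. Is precedence stated?** No. Nothing limits Table 3 to events that are not DLTs or to later cycles. Section 10.1 adds to the confusion by sending the reader to Section 10.3 for dose modifications, which are in Section 10.4.

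**Step 3. Route to the endpoint.** Section 16 requires two consecutive assessments for every response category. Under Section 11.3 the first disease evaluation after baseline is Cycle 2 Day 1. The end-of-treatment list in Section 11.6 has no serum or urine disease evaluation. A patient removed during Cycle 1 therefore has no scheduled route to a confirmed response, and Section 19.4 makes that patient a non-responder in any case. Under Table 3 the scheduled evaluations continue.

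**Step 4. The plan's own figure.** Inputs from Sections 19.1 and 19.4: n = 19, success if X ≥ 9, null rate 0.30, alternative 0.60, one-sided exact binomial test, alpha 0.1.

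- Pr(X ≥ 9) with X ~ Bin(19, 0.30) = 0.0839, within 0.1. A cut-off of 8 would give 0.182.
- Pr(X ≥ 9) with X ~ Bin(19, 0.60) = 0.9115, against a stated 90%. The figure reproduces.

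**Step 5. Illustration.** Assume that k of the 19 are removed under Section 10.3, that none of them can respond, and that each of the other 19 − k responds with probability p. The success probability is Pr(X ≥ 9) with X ~ Bin(19 − k, p).

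| k | p = 0.60 | p = 0.30 |
|---|---|---|
| 0 | 0.912 | 0.084 |
| 1 | 0.865 | 0.060 |
| 2 | 0.801 | 0.040 |
| 3 | 0.716 | 0.026 |

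Removals lower the chance of success at both rates, so the type I error stays within its limit. The documents give no frequency for these events; k = 1 to 3 is an assumed range.

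**The case against.** The best defence is that Section 10.3 is a specific, mandatory rule for Cycle 1 DLTs, while Section 10.4 says modifications are allowed and Table 3 is titled as guidelines with recommended actions. On that reading DLTs go off study and Table 3 covers everything else. This is a sensible reading, but the text does not state it: the sentence leading into Table 3 says its rules will be used, and the Grade 3 rash row has no carve-out for DLTs. What stands is that the gap is one of precedence, and short wording can close it.

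The defence is right to resist several stronger inferences:

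- **That every related Grade 3-4 event is affected.** The attribution threshold and the exception list remove most of the overlap, as Step 1 shows.
- **That Section 10.6.1 extends the conflict to all later cycles.** It is triggered only by a treatment-related chronic toxicity. With no separate definition, a transient Grade 3 rash in a later cycle is not clearly caught. The conflict may continue after Cycle 1, but the text does not settle this.
- **That progression-free survival is altered.** Section 8.2 counts progression or death, so stopping treatment is not itself an event, and no effect has been shown.
- **That the lead-in tally changes.** Sections 10.2 and 19.3 count drug-related toxicity requiring delay or suspension. A hold is a delay and a removal stops treatment, so either plausibly counts. The wording is still untidy, because Section 10.2 also describes the lead-in group as patients without a DLT.
- **That the stated 90% power is wrong.** Section 19.1 gives 60% as the true rate for the combination. Read as an overall rate that already includes Cycle 1 toxicity withdrawals as non-responders, power stays 0.912. Step 5 also assumes that patients kept on at a reduced dose after severe toxicity would respond at the full 60%, which may be generous.

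**Conclusion.** The contradiction is real and limited. For Cycle 1 events that are probably or definitely related and non-excepted (chiefly Grade 3 rash and other Grade 3-4 non-hematological toxicity, with narrow hematological cases), Section 10.3 and Table 3 cannot both be followed, and no precedence is stated. Whether it persists after Cycle 1 depends on what chronic toxicity means in Section 10.6.1.

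The consequence is that the responder count can depend on which passage a site applies. Its size cannot be estimated from the documents. The fall in power from 0.912 to 0.716 with three removals is a conditional illustration that treats 60% as the rate among continuing patients and assumes removed patients cannot respond. It is not a forecast, and no design figure in the plan is shown to be in error.

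**What to change.** Reconcile Section 10.3, Table 3 in Section 10.4.2, and Section 10.6.1. For each overlapping event class, state which passage governs in Cycle 1 and which governs afterwards, and define what counts as a chronic toxicity. Correct the cross-reference in Section 10.1. Which clinical rule should prevail is for the sponsor and investigators; none is proposed here.

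Then align the lead-in wording in Sections 10.2 and 19.3 with the reconciled rule. Section 19.3 repeats the DLT criteria but omits both the attribution threshold and the off-study consequence. Section 19.4 needs no second counting rule: Cycle 1 toxicity withdrawals are already non-responders, and patients who stay on treatment are assessed under Section 16.

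The cost is amendment wording and notice to sites. It needs no extra patients or procedures and no change to the sample size or cut-off.

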#### **10.4. Dose Modifications and Treatment Delays**

Dose modifications are allowed as recommended by the Package Inserts (see **Appendix F**) of the individual study drugs.

**10.4.1. Abatacept**

There is no planned dose modification for abatacept.

**10.4.2. Ixazomib**

The starting dose of ixazomib is 4 mg administered orally once a week on Days 1, 8, and 15 of a 28-day treatment cycle.

Dose reductions due to adverse reactions are as follows:

**Table 2 Ixazomib Dose Reductions**

Dose Level	Dose of Ixazomib
Starting dose*	4 mg
First reduction	3 mg
Second reduction	2.3 mg
Discontinue	-

\* Reduce the starting dose of ixazomib to 3 mg in patients with moderate (total bilirubin greater than 1.5-3 x ULN) or severe (total bilirubin greater than 3 x ULN) hepatic impairment.

The following dose modification rules will be used with respect to potential toxicity. Dose reescalation with Ixazomib will be allowed at the treating Investigators discretion.

**Table 3 Dose Modification Guidelines for Ixazomib**

Hematological Toxicities	Recommended Actions
Thrombocytopenia (Platelet Count)	
Platelet count less than 30,000/mm 	
 
Withhold ixazomib until platelet count is at least 30,000/mm^3.
 
Following recovery, resume ixazomib at the next lower dose.
 

Neutropenia (Absolute Neutrophil Count)	
Absolute neutrophil count less than 500/mm 	
 
Withhold ixazomib until absolute neutrophil count is at least 500/mm^3. Consider adding G-CSF as per clinical guidelines.
 
Following recovery, resume ixazomib at the next lower dose.
 

Non-Hematological Toxicities	Recommended Actions
Rash	
Grade † 2 or 3	
 
Withhold ixazomib until rash recovers to Grade 1 or lower.
 
Following recovery, resume ixazomib at the next lower dose.
 

Grade 4	
 
Discontinue treatment regimen.
 

Peripheral Neuropathy	
Worsening Peripheral Neuropathy over Baseline (Grade 2 with pain or Grade 3)	
 
Reduce ixazomib to the next lower dose. Reevaluate after 1 cycle, if improved or stable, continue at the reduced dose.
 

Grade 4 Peripheral Neuropathy	
 
Discontinue treatment regimen.
 

Other Non-Hematological Toxicities	
Other Grade 3 or 4 Non-Hematological Toxicities	
 
Withhold ixazomib. If attributable to ixazomib, resume at the next lower dose following recovery.
 

†Grading based on National Cancer Institute Common Terminology Criteria (CTCAE) Version 5.0.

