### **3. INCLUSION AND EXCLUSION CRITERIA**

#### **3.1. Inclusion Criteria**

To be included in this study, participants must meet the following criteria:

1. Patients with multiple myeloma who have relapsed (or who are primary refractory) following treatment with a proteasome inhibitor-containing regimen (excluding ixazomib), and who have not been treated with a second proteasome inhibitor (ixazomib, bortezomib, carfilzomib, or other proteasome inhibitor).
2. Age  $\geq$  18 years of age at time of consent.
3. Have an ECOG Performance Status of  $\leq$  2 at study entry. Refer to **Appendix A**.
4. Must be free of systemic infection:
  - Subjects with active infections (whether or not they require antibiotic therapy) may be eligible after complete resolution of the infection.
  - Subjects on antibiotic therapy must be off antibiotics for at least 7 days before beginning treatment.
5. Have the following clinical laboratory values:
  - Absolute neutrophil count  $\geq$  750/mm^3
  - Platelet count  $\geq$  25,000/mm^3
  - Creatinine clearance  $\geq$  30 mL/min
  - Total bilirubin: AST (SGOT) and ALT (SGPT)  $\leq$  3x ULN
6. Patient's multiple myeloma cells are positive for CD28 or CD86 expression by flow cytometry or immunohistochemistry (in any proportion). CD28 or CD86 positivity can have been determined on previous bone marrow aspirates or biopsies.
7. Disease free of prior malignancies for  $>2$  years with exception of currently treated basal cell, squamous cell carcinoma of the skin, or carcinoma "in situ" of the cervix or breast.
8. Participants of child-bearing potential must agree to use adequate contraceptive methods (e.g., hormonal or barrier method of birth control; abstinence) prior to study entry. Should a woman become pregnant or suspect she is pregnant while she or her partner is participating in this study, she should inform her treating physician immediately.
9. Participant must understand the investigational nature of this study and sign an Independent Ethics Committee/Institutional Review Board approved written informed consent form prior to receiving any study related procedure.

Refer to **Appendix B** for the ELIGIBILITY VERIFICATION FORM: INCLUSION CRITERIA CHECKLIST.

Roswell Park Protocol No.: I 47217

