### **19.3. Safety Cohort**

A safety lead-in cohort of  $n_1=6$  patients will be enrolled and, after each patient completes at least 1 cycle of the treatment regimen, the study will be suspended and evaluated for the safety/tolerability of the regimen. If 0 or 1 patient out of 6 has experienced a drug related toxicity requiring treatment delay or suspension, then an additional  $n_2=13$  patients are enrolled to complete the study. Otherwise, the study will be suspended and the research team will meet to discuss possible safety concerns and will decide what actions to take with respect to study continuation.

DLTs are AEs that occur within Cycle 1 and meet any of the following criteria:

1. Treatment-emergent Grade 4 or 5 AE related to ixazomib + abatacept + dex treatment (see exceptions listed in #4 below).
2. Treatment-emergent Grade 3 AE related to ixazomib + abatacept + dex (see exceptions listed in # 4 below).
3. Treatment-emergent Grade 3 seizures.
4. The following will not be considered DLTs:
  - o Non-hematologic AEs
    - Grade 3 fatigue lasting  $\leq 7$  days.
    - Grade 3 or 4 fever or febrile neutropenia for  $\leq 2$  weeks.
    - Grade 3 increase in transaminases for  $\leq 2$  weeks or Grade 4 increase in transaminases for  $\leq 7$  days.
    - Grade 3 Tumor Lysis Syndrome (TLS) for  $\leq 2$  weeks.
    - Grade 3 or 4 asymptomatic, non-hematological clinical laboratory abnormalities that return to  $\leq$  Grade 2 within 7 days or electrolyte abnormalities that resolve with replacement.
    - Grade 3 diarrhea lasting  $\leq 72$  hours that does not require total parenteral nutrition (TPN), tube feeding, or hospitalization, and the toxicity resolves to

less than grade 3 within 72 hours.

- Grade 3 nausea/vomiting lasting  $\leq$  72 hours that does not require total parenteral nutrition (TPN), tube feeding, or hospitalization, and the toxicity resolves to less than grade 3 within 72 hours.
- Grade 3 peripheral neuropathy.
- Grade 3 hyperglycemia or Grade 4 that responds to insulin therapy.
- Hematologic AEs
  - Grade 3 neutropenia of any duration or Grade 4 neutropenia lasting  $<$  14 days.
  - Grade 3 or 4 lymphopenia.
  - Grade 3 or 4 leukopenia.
  - Grade 3 or 4 thrombocytopenia without bleeding or requiring platelet transfusion.
  - Grade 3 or 4 anemia.
  - Grade 3 or 4 B-cell aplasia and hypogammaglobulinemia.

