			5. Have the following clinical laboratory values: 
 
Absolute neutrophil count <math>\geq</math> 750/mm^3
 
Platelet count <math>\geq</math> 25,000/mm^3
 
Creatinine clearance <math>\geq</math> 30 mL/min
 
Total bilirubin: AST (SGOT) and ALT (SGPT) <math>\leq</math> 3x ULN
 
	
			6. Patient's multiple myeloma cells are positive for CD28 or CD86 expression by flow cytometry or immunohistochemistry (in any proportion). CD28 or CD86 positivity can have been determined on previous bone marrow aspirates or biopsies.	
			7. Disease free of prior malignancies for $>2$ years with exception of currently treated basal cell, squamous cell carcinoma of the skin, or carcinoma "in situ" of the cervix or breast.	
			8. Participants of child-bearing potential must agree to use adequate contraceptive methods (e.g., hormonal or barrier method of birth control; abstinence) prior to study entry. Should a woman become pregnant or suspect she is pregnant while she or her partner is participating in this study, she should inform her treating physician immediately.	

Roswell Park Protocol No.: I 47217

INCLUSION CRITERIA				
Yes	No	N/A	All answers must be "Yes" or "N/A" for participant enrollment.	Date
			9. Participant must understand the investigational nature of this study and sign an Independent Ethics Committee/Institutional Review Board approved written informed consent form prior to receiving any study related procedure.	

Investigator Signature: \_\_\_\_\_ Date: \_\_\_\_\_

Printed Name of Investigator: \_\_\_\_\_

Roswell Park Protocol No.: I 47217

**Appendix C ELIGIBILITY VERIFICATION FORM  
EXCLUSION CRITERIA**

**Participant Name: (Multi-site: use participant initials):** \_\_\_\_\_

**Medical Record No.: (Multi-site: use participant ID):** \_\_\_\_\_

**Title:** Phase II Study of Targeting CD28 in Multiple Myeloma with Abatacept (CTLA4-Ig) to Overcome Resistance to Chemotherapy

EXCLUSION CRITERIA			
Yes	No	N/A	All answers must be "No" or "N/A" for participant enrollment.

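### Entry admits platelet counts of 25,000 to 29,999/mm³, but Table 3 withholds ixazomib below 30,000/mm³ and does not say how a count already low at baseline is handled

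*Combined protocol and SAP*

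**What the plan says.** Section 3.1, criterion 5, sets the platelet limit for entry at 25,000/mm³ or more and the neutrophil limit at 750/mm³ or more. The checklist in Appendix B repeats both.

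Section 10.4.2 gives the planned dose: "The starting dose of ixazomib is 4 mg administered orally once a week on Days 1, 8, and 15" of each 28-day cycle. The one exception to the starting dose is the hepatic footnote to Table 2: "Reduce the starting dose of ixazomib to 3 mg in patients with moderate" or severe hepatic impairment. Nothing comparable is given for platelets.

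The platelet row of Table 3 is triggered by "Platelet count less than 30,000/mm 3". Two actions follow: "Withhold ixazomib until platelet count is at least 30,000/mm" (cubed millimetre), and "Following recovery, resume ixazomib at the next lower dose". The neutrophil row has the same structure, with a limit of 500/mm³.

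The lead-in rule in Sections 10.2 and 19.3 lets the study continue if no more than one of six patients "has experienced a drug related toxicity requiring treatment delay or suspension". Under Section 19.4 the combination is considered promising if 9 or more of 19 patients respond.

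**The concern.** A patient can satisfy the entry criterion and, with no change in count, satisfy the condition for stopping one of the three study drugs. The protocol does not say what a site should do with that patient.

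Two things are at stake. The first is uniform treatment: this is a multi-site study, and different sites could reasonably give full dose, hold or reduce. The second is interpretation. A patient held or reduced because of the baseline count has not received ixazomib as planned, yet contributes a full observation to the verdict on the three-drug combination. For someone whose usual count is below 30,000/mm³, the condition for resuming may never be met, and the platelet row offers no other way back to dosing.

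**Working it through.** No figure in the plan depends on this point, so the check is a comparison of limits and of wording.

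**Limits**

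| Count (per mm³) | Entry (Section 3.1, Appendix B) | Hold (Table 3) | Eligible and on hold |
|---|---|---|---|
| Platelets | ≥ 25,000 | < 30,000 | 25,000 to 29,999 |
| Neutrophils | ≥ 750 | < 500 | none |

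The platelet overlap is 30,000 − 25,000 = 5,000/mm³ wide. For neutrophils the entry limit lies 750 − 500 = 250/mm³ above the hold limit, so the mismatch is confined to platelets.

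**Wording within Table 3.** The peripheral neuropathy row is tied to worsening relative to baseline. The row for other Grade 3 or 4 non-hematological toxicities makes the dose reduction depend on attribution to ixazomib. The platelet row has neither qualifier.

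**Timing.** Section 11.3 schedules a blood count on Day 1 of each cycle and Section 11.5 on Days 8, 15 and 22 of Cycle 1. Take an eligible patient with 27,000/mm³ at baseline and no change afterwards:

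1. Entry: 27,000 ≥ 25,000, so eligible.
2. Day 1: the planned dose is 4 mg, and no starting-dose exception applies.
3. Day 8, the first on-treatment count: 27,000 < 30,000, so the hold condition is met with no drug effect.
4. Release: requires 30,000 or more. If reached, Table 2 gives 3 mg as the next lower dose. If not reached, the row gives no further instruction.

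**Weight in the primary analysis.** Section 19 includes everyone who receives or attempts to receive treatment. Section 19.4 replaces only patients who withdraw before completing Cycle 1 for reasons unrelated to treatment; being on hold is not withdrawal. Each patient therefore counts as 1/19 = 5.3 percentage points of the observed response rate, against a decision limit of 9/19 = 47.4%. This is a patient's weight in the analysis, not an estimate of lost responses.

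**The case against.** **Table 3 is about toxicity.** Section 10.4.2 introduces the reductions as responses to adverse reactions and the rules as concerning potential toxicity. The rows are headed as toxicities, the actions are recommendations, and to resume presupposes earlier dosing. A reader might infer that the entry criterion and the dose table collide at the first dose. The documents do not support that: on this framing an untreated patient with a low count need not trigger Table 3 on Cycle 1 Day 1. This part of the objection stands. It does not settle Day 8, when the patient has been dosed, the trigger is still a bare count, and an unchanged or slightly lower value must be classified. Section 13.2 lists thrombocytopenia among the most frequent events with ixazomib, so attribution will not be obvious.

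**The lead-in is largely protected.** A reader might also infer a substantial effect on the 0-or-1-of-6 rule. If one of the six were counted as an event because of the baseline count, the probability of meeting the rule would fall as follows, with p the true event rate in the others:

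- p = 0.2: from 0.8⁶ + 6 × 0.2 × 0.8⁵ = 0.655 to 0.8⁵ = 0.328
- p = 0.1: from 0.9⁶ + 6 × 0.1 × 0.9⁵ = 0.886 to 0.9⁵ = 0.590

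The arithmetic is right, but the documents do not support it as a consequence of the plan. Section 17.1 defines an adverse event as new or worsening, Section 17.1.4 records a preexisting condition only if it worsens, and Section 19.5 defines a toxicity as an adverse event at least possibly related to treatment. Together these imply that an unchanged baseline count is not a lead-in event. The figures require an assumed patient in the range, among the first six, and miscounted. Failing the rule also leads to suspension and a team review, not automatic termination.

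**Other mitigations.** Section 10.4.2 allows re-escalation at the investigator's discretion, so a reduction need not last. Sections 10.4 and 32 also refer dose modification to the package inserts, which Appendix F only links. The statement that no exception exists therefore covers the protocol text alone. Exclusion 8 allows a patient to be kept out because of laboratory abnormalities, but it does not say how one who is admitted should be dosed.

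**Conclusion.** The inconsistency is real but limited. Patients with 25,000 to 29,999 platelets/mm³ are eligible, and one who stays there meets the Table 3 hold condition at the first on-treatment count without any drug effect. The protocol text does not resolve the case. Such a patient would count toward the 9-of-19 decision, possibly without the planned ixazomib exposure.

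The documents give neither the number of such patients nor the effect of reduced exposure on response, so the size of the effect is unknown. Any lead-in effect would arise only from misattribution. The case for acting is that the rule, read literally, withholds and reduces study drug in eligible patients who have had no toxicity, and that clarifying it is cheap.

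**What to change.** Section 3.1 criterion 5, the Appendix B checklist and the platelet row of Table 3 must be reconciled, so that the entry criterion and the dose rule agree on how a count already below 30,000/mm³ at baseline is handled. The lead-in rule in Sections 10.2 and 19.3 should then be made consistent with that resolution. Which threshold, dose or counting rule to adopt is for the sponsor and the investigators; none is proposed here.

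The cost is amendment wording in these places. The sample size and the 9-of-19 rule need not change for the clarification itself.
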